Title	A Multi-Center, Randomized, Placebo Controlled, Safety, Tolerability, and Efficacy Trial of a New Botanical Drug Product Containing East Indian Sandalwood Oil (EISO) at One Dose Level for the Treatment of Mild-to-Moderate Plaque Psoriasis in Adult Subjects
Setting and Trial Center	This trial will be conducted at approximately 5 study centers in the United States.
Number of Subjects	Up to 72 to ensure 60 complete the trial
Objectives	
The objectives of this trial are:
 
• To evaluate the safety of SAN021 when administered to adult subjects with mild-to-moderate plaque psoriasis• To evaluate the tolerability of SAN021 when administered to adult subjects with mild-to-moderate plaque psoriasis• To evaluate the preliminary efficacy of SAN021 when administered to adult subjects with mild-to-moderate plaque psoriasis
Trial Design and Patient Population	
This trial will be a multi-center, randomized, placebo controlled study to evaluate the safety, tolerability, and efficacy of SAN021 when administered for up to 42 days to adults between the ages of 18 to 65 years who have a clinical diagnosis of mild-to-moderate plaque psoriasis.
 
Subjects will enter the Screening Period once the informed consent and consent process has been completed. Subjects with mild-to-moderate plaque psoriasis, as defined by a Psoriasis Area and Severity Index (PASI) score between 2 and 12,³⁶ appropriate for topical treatment that covers a minimum of 1.0% and a maximum of 10% BSA, in the permitted treatment areas, and who meet all of the inclusion and none of the exclusion criteria will be enrolled.
 
Once patient eligibility is confirmed and the screening procedures completed, all enrolled subjects will start the Treatment Period of the study. All enrolled subjects will receive either 10% SAN021 or placebo serum (randomized in a 2:1 ratio) with the first dose applied at the Day 1 Study Visit. Subjects will be instructed on how to apply the study medication twice daily for 42 days. Subjects will return to the clinic for study-related assessments on Study Days 8, 15, 28 and a final visit on Day 42. On Study Day 49, patient will receive a Follow-up phone call and be queried for condition status since going off study.

Inclusion Criteria	Subjects will be included in the trial if they meet all of the following

criteria:

1. Are ≥ 18 but ≤ 65 years of age
2. Have a clinical diagnosis of mild-to-moderate plaque psoriasis, as defined by a Psoriasis Area and Severity Index (PASI) score between 2 and 12,³⁶ appropriate for topical treatment that covers a minimum of 1.0% and a maximum of 10% BSA, in the permitted treatment areas.
3. Are willing to treat all psoriasis occurring in the permitted treatment areas with only SAN021
4. Are free of any systemic or dermatologic disorder, which, in the opinion of the investigator, will interfere with the study results or increase the risk of adverse events.
5. Are willing to avoid prolonged exposure of the treatment area to ultraviolet radiation (natural or artificial) for the duration of the study.
6. Are willing to refrain from using any lotions, moisturizer, cleansers, cosmetics or creams, other than those issued as part of the study, on the treatment areas during the treatment period.
7. If female of childbearing potential, must be willing to practice an acceptable form of birth control for the duration of the study.(i.e. oral contraceptive, barrier method and/or intra-uterine device)
8. Are able to give written informed consent in a manner approved by the Institutional Review Board or Ethics Review Committee and comply with the requirements of the study.
9. Are willing to avoid participation in any other clinical trial for the duration of this study.
10. Are willing to refrain from treating restricted areas, which will be excluded from PGA assessment and BSA calculation. These areas are as follows: head, neck, fingernails, toenails, soles of feet, and palms of hands, axillae, or intertriginous areas.

Exclusion Criteria	
Subjects will be excluded from the trial if they meet any of the following criteria:
 
1. Have spontaneously improving or rapidly deteriorating plaque psoriasis, or pustular psoriasis as determined by the Investigator.2. Have been treated, with prescription medication for plaque psoriasis, within 60 days prior to the Baseline visit.3. Are pregnant, breast-feeding, or planning to become pregnant during the study.4. Have any evidence of systemic cancer, squamous cell carcinoma, basal cell carcinoma, in the past 5 years, or any other confounding skin condition.5. Are undergoing treatments with topical antipsoriatic drug products other than corticosteroids within 14 days prior to the Baseline Visit, and for therapy containing corticosteroids or retinoids within 28 days prior to Baseline Visit.6. Have open sores or open lesions in the treatment area(s).7. Have any condition that, in the opinion of the investigator, would confound the safety and/or efficacy assessments of plaque psoriasis.8. Have participated in any interventional clinical trial in the previous 30 days.9. Have a known sensitivity to any of the constituents of the test product including sensitivities to sandalwood oil, fragrances, or any member of the Compositae family of vascular plants (e.g., sunflowers, daisies, dahlias, etc.).10. Have used, are using, or are planning to use immunosuppressive or immunomodulatory medication (i.e., biologics), including oral or parenteral corticosteroids.11. Have a history of alcohol or illegal drug/substance abuse, or suspected alcohol or illegal drug/substance abuse in the past two years.12. Plan to seek alternative treatment of any kind for their psoriasis, in the eligible treatment areas or otherwise, during the trial period.
---------------------------	---

Screening (Day -7)	Eligible subjects will be asked to read and sign an informed consent and photography consent form. No study procedures will be conducted until the informed consent and photography consent forms are signed.
---------------------------	---

At the Screening Visit, the following procedures will be performed:

- Conduct the informed/photography consent process.
- Record Demographics to include age, sex, and race.
- Review the inclusion/exclusion criteria.
- Record all concomitant medications including all prescription drugs, nonprescription drugs, and nutritional supplements taken in the 60-days prior to Screening.
- Perform a full physical examination including height (cm) and weight (kg).
- Record pertinent medical history including tobacco, illegal substance and alcohol history and current use.
- Administer the Physician's Global Assessment (PGA) and the Psoriasis Area Severity Index (PASI).
- Calculate the plaque BSA of the area(s) to be treated.

Treatment Period

Visit 1 Baseline (Day 1 [± 2 Days])

Eligible subjects will have the following procedures completed at Visit 1 (Baseline). It is possible for the patient to be screened and complete the Visit 1 (Baseline) procedures on the same day.

- Review inclusion and exclusion criteria to ensure the patient qualifies for the study.
- If this visit is NOT combined with the screening visit:
 - Perform an abbreviated physical examination including weight (kg),
 - Update concomitant medications including all prescription drugs, non-prescription drugs and nutritional supplements
 - Review and update the patient's pertinent medical history.

- Complete the PGA (only treatment area(s) are to be evaluated), PASI and tolerability assessment (only treatment area(s) are to be evaluated) including calculating the BSA of the affected area (only treatment area(s) are to be evaluated).
- If patient is a female of childbearing potential, collect a urine sample and perform a β -human chorionic gonadotropin pregnancy test.
- Instruct the patient on proper washing of the target treatment area(s) (using only study-approved cleanser) and application of SAN021 study medication on the treatment areas during the treatment period.
- Photograph the treatment area(s).
- Replace the cap with the dropper cap and weigh full bottle of SAN021 study medication and record weight prior to on site first dose.
- With the dropper cap on, weigh bottle of SAN021 study medication post on site dose and dispense to subject.
- Instruct the subject to return in one week for the next study visit with the study drug

Visit 2 (Day 7 [± 2 Days]), Visit 3 (Day 14 [± 2 Days]), Visit 4 (Day 28 [± 2 Days])

All study visits have a ± 2 -day visit window.

- Query for adverse events.
- Update concomitant medications including all prescription drugs, nonprescription drugs, and nutritional supplements.
- Query for treatment regimen compliance.
- Weigh and record the weight of the study medication and re-dispense.
- Complete the PGA (only treatment area(s) are to be evaluated), PASI and tolerability assessment (only treatment area(s) are to be evaluated) including calculating the BSA of the affected area (only treatment area(s) are to be evaluated).
- Photograph the treatment area(s).
- Review the directions for use of the study medication with the patient, and re-educate if applicable.

- Instruct the patient to return for the next study visit with study drug.

Final Visit (Visit 5)

Final Visit (Day 42 [± 2 Days])

- Query for adverse events.
- Update concomitant medications including all prescription drugs, nonprescription drugs, and nutritional supplements.
- Query for treatment regimen compliance.
- Collect and weigh the study medication and record the weight.
- Complete the PGA (only treatment area(s) are to be evaluated), PASI and tolerability assessment (only treatment area(s) are to be evaluated) including calculating the BSA of the affected area (only treatment area(s) are to be evaluated).
- Photograph the treatment area(s).
- Instruct the patient to return for another study visit only if study-related adverse events persist or, in the Investigator's opinion, an additional study visit is warranted to ensure the patient's safety.

Follow-up Call

Follow-up Call (Day 49 [± 2 Days])

- Query for status of condition since going off study
 - i.e. has the condition been stable, worsened or improved since discontinuing study medication?

Duration of Treatment and Trial Participation

The maximum duration of trial participation for each patient is approximately 49 days:

- 7-day Screening Period (Day -7)
- Single-day Baseline Visit 1 (Day 1)
- 42-days of treatment (Visits 2 (Day 7), Visit 3 (Day 14), Visit 4 (Day 28) and Final Visit (Day 42))
- Follow-up Call (Day 49)

If the patient's treatment is interrupted by illness or other

circumstances, every attempt will be made to have the patient return to the clinic for a final visit.

Trial Population	Up to 72 subjects, 18 – 65 years of age inclusive, with a clinical diagnosis of mild-to-moderate plaque psoriasis, as defined by a Psoriasis Area and Severity Index (PASI) score between 2 and 12, ³⁶ that, in the opinion of the investigator, is appropriate for topical treatment, that covers a minimum of 1.0% and a maximum of 10% BSA, in the permitted treatment areas.
Trial Drug, Dose and Mode of Administration	
Study medication will be provided by Santalis Pharmaceuticals.
 
The following treatment product will be provided:
 
▪ SAN021 10% - to be used morning and night, 
OR
 
▪ Placebo- to be used morning and night. 
Subjects will also be provided with:
 
▪ Cetaphil Gentle Skin Cleanser - to be used for the duration of the trial. 
The first treatment of SAN021 will be applied at the Baseline Visit, then patient will be instructed on the procedure for self-administration at home.

Criteria For Evaluation	
Subjects that receive one application of study medication will be included in the safety and tolerability analysis.
 
Subjects that complete at least 80% of treatments, as determined by product usage, will be included in the efficacy analysis.
 
Missing efficacy data will be imputed using the last observation carried forward. No imputations will be made for missing safety data.

Safety Evaluations	
The primary purpose of this study is to determine the safety profile of SAN021.
 
Safety will be assessed by evaluating adverse events (AEs) with respect to severity, duration, and relationship to study drug.

Tolerability Evaluations	Tolerability will be based on the number of subjects reporting discomfort during or immediately following application of SAN021, This will also be recorded as an AE. The study restricted treatment

areas are to be not to be used in this evaluation. (see #10 under Inclusion Criteria)

Preliminary Efficacy Evaluation

Preliminary Efficacy Endpoints:

The preliminary efficacy will be evaluated as follows:

- Percentage of subjects achieving at least a 1-grade improvement in PGA score
- Percentage of subjects achieving a 2-grade improvement in the PGA score
- Percentage of subjects who have a $\geq 25\%$ reduction in the Psoriasis Area and Severity Index (PASI) score at any point during the trial.
- Percentage of subjects who have a $\geq 50\%$ reduction in the Psoriasis Area Severity Index (PASI) score at any point during the trial.
- Number of subjects achieving a Physician's Global Assessment of "clear" or "almost clear" at any time point during the 42 days of therapy. The study restricted treatment areas are not to be included in this evaluation.
(see #10 under Inclusion Criteria)

A. Physician's Global Assessment (PGA): The PGA will be based on a 5-point scale ranging from 0 (clear) to 4 (severe), and will be assessed, preferably by the same evaluator at each visit for the overall affected areas with plaque psoriasis which were treated with the study drug. The study exclusion areas and those areas not treated are not to be used in this assessment. The following scores will be used to describe the severity of overall plaque psoriasis of the treatable areas:

Grade	Score	Description
Clear	0	No signs of psoriasis (post-inflammatory hyperpigmentation may be present)
Almost Clear	1	Intermediate between mild and clear
Mild	2	Slight scaling plaque elevation, scaling, and/or erythema
Moderate	3	Moderate plaque elevation, scaling, and/or erythema
Severe	4	Very marked plaque elevation, scaling, and/or erythema

Data Analysis

Safety

The number and percentage of subjects reporting at least one occurrence of an AE for each unique System Organ Class and Preferred Term will also be tabulated by severity and by the relationship to trial drug. All AEs will be presented in a data listing.

Tolerability

Tolerability will be based on the number of subjects reporting discomfort during or immediately following application of SAN021, this will also be recorded as an AE.

Preliminary Efficacy

The efficacy will be assessed as follows:

- Percentage of subjects achieving at least a 1-grade improvement in PGA score
- Percentage of subjects achieving a 2-grade improvement in the PGA score
- Percentage of subjects who have a $\geq 25\%$ reduction in the Psoriasis Area and Severity Index (PASI) score at any point during the trial.
- Percentage of subjects who have a $\geq 50\%$ reduction in the Psoriasis Area Severity Index (PASI) score at any point during the trial.
- Number of subjects achieving a Physician's Global Assessment of "clear" or "almost clear" at any time point during the 42 days of therapy. The study restricted treatment areas are not to be included in this evaluation. (see #10 under Inclusion Criteria)

Planned Dates of Study

April 2017 to December 2017

Trial Contacts

Name	Affiliation / Address	Responsibility
Santalis Pharmaceuticals	[name]  [contact]  [contact]	Sponsor
[name], PhD	Santalis Pharmaceuticals [name]  [contact]  [contact] e-mail: [contact]	Sponsor Representative

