## 8.2 Psoriasis Area and Severity Index

The PASI is a continuous measure of psoriasis severity with scores that can range from 0 to 72 with higher scores indicating more severe conditions. For this study the population is required to have PASI scores between 2 and 12, inclusive, at baseline. Scores will be summarized by visit with n, mean, SD, median, minimum, and maximum. Change from baseline will be calculated (follow-up value – baseline value) and summarized by follow-up visit. Change values that are negative represent an improvement. Percent change from baseline ((follow-up value – baseline value)/baseline value) x 100 will also be summarized by follow-up visit.

Percent change from baseline will be assigned to one or more of the following categories:

Group	Percent Reduction Category	Percent change from baseline values
1	< 25% Reduction	$> -25.0$
2	$\geq 25\%$ Reduction	$\leq -25.0$
3	$\geq 50\%$ Reduction	$\leq -50.0$
4	$\geq 75\%$ Reduction	$\leq -75.0$

These groups are not mutually exclusive; results that fall into group 4 will also be counted in groups 2 and 3, likewise results that fall into group 3 but not group 4 will also be counted in group 2. The frequency distribution of subjects within each of these groups will be summarized by visit. A summary over all follow-up visits will include the number and percent of subjects achieving their best (lowest value/greatest reduction) percent change at any time point during the 42 days of therapy.

The results will be presented in a by-subject listing.

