## 9.0 CONVENTIONS FOR CALCULATIONS AND TABULATIONS

*Table 9.0 Conventions for Calculations and Tabulations*

CONVENTION	DESCRIPTION
Age calculation	Age is calculated as an integer in years as the difference between the subject's date of informed consent and the date of birth. Specifically, if a subject's birthday has been reached by the informed consent date then age will be the difference in years, otherwise age will be the difference in years minus 1.
Baseline	Baseline is defined as assessments completed on Visit 1 (Day 1) prior to the administration of the study drug unless otherwise specified.
Study Day	Date of visit or evaluation – baseline date + 1
Percentage calculation	Percentages are calculated as 100* numerator/denominator. Rounding is not necessary because rounding is handled by the display format. Denominator is the total number of subjects in a column group unless otherwise specified.
AE counting: treatment emergence	An AE will be considered treatment emergent if it begins on or after the time of the first study treatment application. If the start date is the same as the date of first application (Day 1), the times are not present, or there is no indication that the AE began before dosing, the event will be considered treatment emergent.
AE counting: general summary	In summary displays, AEs are counted only once per subject within a category (e.g., over all and preferred term).
AE counting: summary by assessment	When AEs are summarized within levels of another AE assessment (e.g., causality or severity), AEs are counted once per subject at the worst level of the assessment (e.g., least

CONVENTION	DESCRIPTION
	complementary relationship or greatest severity). A missing or unknown value for the assessment will be considered worst.
Change from Baseline	current visit value – baseline visit value
Percent Change from Baseline	((current visit value —baseline visit value) / baseline visit value) x 100

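### Is the skin area scored for PASI left so open that the 25% and 50% response endpoints are undefined?

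*Protocol*

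**What the plan says.** Inclusion Criterion 10 sets aside the skin that is not to be treated (head, neck, nails, palms, soles, axillae, intertriginous areas). It says of subjects: "Are willing to refrain from treating restricted areas, which will be excluded from PGA assessment and BSA calculation". Inclusion Criterion 3 has all psoriasis in the permitted areas treated, so treated and permitted skin coincide by design.

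The Screening list says: "Administer the Physician's Global Assessment (PGA) and the Psoriasis Area Severity Index (PASI", with no area given for either scale. The Visit 1 (Baseline) list says: "Complete the PGA (only treatment area(s) are to be evaluated), PASI and tolerability assessment (only treatment area(s) are to be evaluated", and the lists for Visits 2 to 4 and the Final Visit repeat that wording. Screening and Baseline may be combined: "It is possible for the patient to be screened and complete the Visit 1 (Baseline) procedures on the same day".

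The protocol's efficacy endpoint list ends with: "The study restricted treatment areas are not to be included in this evaluation". That sentence follows the clear/almost-clear endpoint; the two PASI items state no area.

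SAP 8.2 says: "The PASI is a continuous measure of psoriasis severity with scores that can range from 0 to 72" and "For this study the population is required to have PASI scores between 2 and 12, inclusive, at baseline". It does not say which skin is scored. SAP Table 9.0 says: "Baseline is defined as assessments completed on Visit 1 (Day 1) prior to the administration of the study drug unless otherwise specified".

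**The concern.** A list that names PGA and BSA and leaves out PASI invites the reading that PASI is not restricted. The PASI endpoints state no area, and SAP 8.2 quotes the full range of the scale. A site could then score the whole body while PGA and BSA are confined to treated skin.

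Disease on the restricted areas receives no study product, and Exclusion Criterion 12 bars other treatment there too. Under whole-body scoring, that stable disease stays in both the numerator and the denominator and dilutes the percent reduction. A subject whose treated skin improves by exactly 50% would count as a responder at one site and not at another, and about five sites are pooled in one table.

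The more serious worry is a mixed score: whole body at entry, carried into Baseline when the two visits share a day, then treated skin at follow-up. PASI would then fall in both arms with no drug effect.

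**Working it through.** The plan has no figure to reproduce here. SAP 2.2 states that there is no formal sample size assessment and no inferential analysis. The check has two parts.

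**Which readings the text supports**

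1. *Visit lines.* PGA and BSA each have their own area limit. PASI and tolerability are joined and share one. If that limit covered tolerability alone, PASI would be the only assessment in the line with no limit. The natural reading is treated areas only.
2. *Screening line.* It gives no area for PASI, but none for PGA either, and Criterion 10 plainly restricts PGA. Silence there is not evidence of a whole-body PASI.
3. *SAP.* Section 8.2 has no area rule, but neither have 8.1 (PGA) and 8.3 (BSA), both restricted by the protocol. The SAP leaves the scored area to the protocol for all three measures. The 0 to 72 sentence describes the scale.
4. *Mixed score.* Baseline and follow-up share the same PASI wording. In the Visit 1 list, the items that depend on the visit not being combined with Screening are the abbreviated examination, the medication update and the history update. PASI is outside that group, so it is completed under the Visit 1 instruction even on a combined day. SAP Table 9.0 takes baseline from Visit 1. Nothing in the text prescribes a whole-body baseline with treated-area follow-up.

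Two readings remain: (A) treated areas throughout, the natural one, and (B) whole body throughout.

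**How far A and B differ**

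Input: f, the share of baseline PASI on restricted skin, assumed stable and equal for all subjects. The documents give no value; 0 to 30% is shown.

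- Whole-body reduction = (1 − f) × treated-skin reduction.
- Treated-skin reduction needed for a PASI reduction of T is T/(1 − f).
- The between-arm difference in mean percent change is multiplied by (1 − f).

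| f | needed for 25% | needed for 50% | multiplier |
|---|---|---|---|
| 0 | 25.0% | 50.0% | 1.0 |
| 10% | 27.8% | 55.6% | 0.9 |
| 20% | 31.3% | 62.5% | 0.8 |
| 30% | 35.7% | 71.4% | 0.7 |

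An illustration at f = 20% takes treated-skin reductions as normal with means 50 (active) and 25 (placebo) and SD 25, all assumed. The responder rate is P(reduction > needed value).

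- 50% response: A gives 50.0% against 15.9%, a difference of 34.1 points; B gives 30.9% against 6.7%, a difference of 24.2 points.
- 25% response: A gives 84.1% against 50.0%, a difference of 34.1 points; B gives 77.3% against 40.1%, a difference of 37.2 points.

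The effect of B is thus not in one direction. The illustration uses one reduction per subject, whereas the endpoint is the best value at any visit, so it shows scale only.

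For completeness, the mixed score would show a reduction of f with no true change (10%, 20% or 30%) and would meet the 25% criterion without improvement once f reaches 25%. It would take a departure from the Visit 1 instruction to produce it.

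**The case for a change.** The best case for a change is that a natural reading of one line is not a rule. Criterion 10 names two of the three measures, the protocol gives PGA its own explicit area statement and PASI none, and the closing sentence of the endpoint list may belong to clear/almost clear alone. Sites could differ in good faith. Entry could be touched too: with f = 20%, a whole-body PASI of 2.4 is 2.4 × 0.8 = 1.92 on treated skin, below the minimum of 2. Writing the rule down costs one sentence, and settling it after unmasking could look driven by results.

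It stands that the PASI area is never stated outright and that A and B can classify the same subject differently. It does not stand that the documents contradict each other: they are silent or loosely punctuated. If the closing sentence of the endpoint list covers the whole list, it supports treated areas. The supplied protocol text is also a synopsis. SAP 3.4 refers to an intent-to-treat definition in the protocol that the supplied text does not contain, so scoring instructions may exist elsewhere.

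**Conclusion.** No change to the plan follows. This is a gap in wording that raters and analysts fill sensibly from the visit lines: PASI on treated areas, scored alike at Baseline and follow-up. On that reading the two PASI response endpoints mean what they say, and they match the area used for PGA and BSA. No stated rule gives a wrong result.

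If a site did score the whole body throughout, the treated-skin reduction needed for a 50% response would rise from 50% to 55.6%, 62.5% or 71.4% at f = 10%, 20% or 30%, with no effect at f = 0. These figures rest on an assumed f and on stable restricted-area disease. The scoring rule would be the same in both randomised arms, safety is the primary objective, and the efficacy summaries are descriptive, so no error rate or power is at risk. A clarifying sentence in the scoring instructions would be good housekeeping, but it would not alter the planned analysis.

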## 2.0 STUDY DESIGN

### 2.1 Overview of Study Design

This trial will be a double blind, multi-center, randomized, placebo controlled study to evaluate the safety, tolerability, and efficacy of SAN021 when administered topically for up to 42 days to adults between the ages of 18 to 65 years inclusive who have a clinical diagnosis of mild-to-moderate plaque psoriasis. Subjects will enter the Screening Period once the informed consent and photographic consent process has been completed. Subjects with mild-to-moderate plaque psoriasis, as defined by a PASI score between 2 and 12, that, in the opinion of the investigator, is appropriate for topical treatment, covers a minimum of 1.0% and a maximum of 10.0% body surface area in the permitted treatment areas, and who meet all of the inclusion and none of the exclusion criteria will be enrolled.

Once subject eligibility is confirmed and the screening procedures completed, all enrolled subjects will start the Treatment Period of the study. All enrolled subjects will receive either 10% SAN021

or placebo serum (randomized in a 2:1 ratio) with the first dose applied at the Day 1 Study Visit. Subjects will be instructed on how to apply the study medication twice daily for 42 days. Subjects will return to the clinic for study-related assessments on Study Days 7, 14, 28 and a final visit on Day 42. On Study Day 49, subjects will receive a follow-up phone call and be queried for condition status since going off study.

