## 7.1 Adverse Events

An AE is any reaction, side effect, or other untoward event, regardless of relationship to study drug, that starts any time after the beginning of dosing. Non-serious AEs will be captured through the last treatment application, Day 42/exit, and serious AEs will be captured up through 28 days following the discontinuation of therapy.

All AEs reported will be considered to be treatment-emergent. Verbatim adverse events will be mapped to PT and SOC using MedDRA 19.0.

Tabular summaries of treatment-emergent adverse events (TEAEs) in terms of number of subjects will be presented by each study arm for the following:

- PT presented in order of descending incidence in the SAN021 group then alphabetically
- SOC and PT presented in order of descending incidence in SOC, then PT, in the SAN021 group, then alphabetically by SOC and PT
  - repeat presentation for subset of study-drug related events
- SOC, PT, and maximum severity grade (mild, moderate, severe) presented alphabetically by SOC and PT

Adverse events will be counted as treatment related if they are evaluated as possibly, probably, or definitely related to study treatment. Subjects will be counted once within each level of summarization within each study arm for the calculation of incidence.

A summary of count and percent of subjects with at least one event in the following categories will be tabulated: any TEAE, any mild TEAE, any moderate TEAE, any severe TEAE, any treatment-related TEAE, any serious TEAE, any TEAE that led to discontinuation of study drug, and any deaths.

A comprehensive listing of all AEs will be provided by subject, which will include the duration of each event. Duration will be calculated as the stop date of the event minus the start date, unless the event is determined ongoing at exit.

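### The SAP's serious-AE window runs to about Day 70, but the visible schedule has no AE question after Day 42

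*Protocol*

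**What the plan says.** SAP 7.1 sets two capture windows. For the milder class, "Non-serious AEs will be captured through the last treatment application, Day 42/exit"; for the other, "serious AEs will be captured up through 28 days following the discontinuation of therapy". It then states that "All AEs reported will be considered to be treatment-emergent", and its summary of TEAEs includes "any serious TEAE, any TEAE that led to discontinuation of study drug, and any deaths". SAP Table 10.2 lists that summary as Table 14.3.1.1.

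The protocol synopsis lists an adverse event query at Visits 2 to 4 and at the Final Visit on Day 42. For the Day 49 call it lists one item, "Query for status of condition since going off study", explained as whether the psoriasis has stayed the same, become worse or become better. SAP 2.1 agrees: "On Study Day 49, subjects will receive a follow-up phone call and be queried for condition status since going off study".

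The synopsis also says that "The maximum duration of trial participation for each patient is approximately 49 days", and SAP Table 2.1 ends with the call. Two clauses allow more follow-up. At the Final Visit sites are to "Instruct the patient to return for another study visit only if study-related adverse events persist", or if the investigator thinks a further visit is needed for safety. Note 2 to SAP Table 2.1, attached to the call, lets follow-up run on where an adverse event needs longer to assess.

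**The concern.** The SAP promises serious-AE capture for four weeks after treatment, but the listed contacts stop asking about adverse events on the day treatment ends. Suppose a subject is admitted to hospital on Day 55 for something the subject thinks unrelated. SAP 7.1 counts adverse events whatever their relationship to study drug, so the event belongs in the tables. Nothing in the visible schedule would bring it to the site's attention.

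Safety is the primary objective (SAP 1.1.1). A reader who sees a zero for serious TEAEs or deaths in Table 14.3.1.1, next to a 28-day window, could take it as 70 days of equally complete follow-up. What is at stake is the completeness of serious-event counts after treatment. The evidence on the treatment period itself is not in question.

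**Working it through.** The plan gives the length of the window but not its end day, so there is no stated figure to reproduce.

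**Inputs**
- Treatment: 42 days (protocol synopsis; SAP 2.1).
- Serious-AE window: 28 days after therapy stops (SAP 7.1).
- Last listed AE query: Day 42 ± 2 (protocol, Final Visit).
- Last scheduled contact: Day 49 ± 2 (protocol, Follow-up Call; SAP Table 2.1).
- Subjects: up to 72, to obtain 60 completers.

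**Nominal timing, subject treated to Day 42**
- End of window: 42 + 28 = Day 70.
- No scheduled AE query: Days 43 to 70 = 28 days; 28/70 = 40%.
- No scheduled contact: Days 50 to 70 = 21 days; 21/70 = 30%.
- Reachable by a question on the call: Days 43 to 49 = 7 days; 7/28 = 25% of the window.

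**With the ±2-day windows**, taking the last application as the Final Visit (Day 40 to 44) and the call as Day 47 to 51:
- End of window: 40 + 28 = Day 68 to 44 + 28 = Day 72.
- Reachable by the call: 47 − 44 = 3 days to 51 − 40 = 11 days, or 11% to 39% of 28.
- Left after the call: 28 − 11 = 17 to 28 − 3 = 25 days.

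**Early discontinuation** brings the end of the window forward: stopping on Day 28 gives 28 + 28 = Day 56, and stopping on Day 14 gives Day 42. The figures above are for subjects treated to Day 42.

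**Subject-days without an AE query**
- All 72 treated to Day 42: 72 × 28 = 2,016. The call could cover 72 × 7 = 504.
- 60 completers: 60 × 28 = 1,680. The call could cover 60 × 7 = 420.

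**Likely number of events.** The documents give no background rate. Assume 1 to 5 serious AEs per 100 subject-years, purely to show scale.
- Whole window: 2,016 / 365.25 = 5.5 subject-years, so 0.06 to 0.28 expected events in both arms together.
- Part covered by the call: 504 / 365.25 = 1.4 subject-years, so 0.01 to 0.07.

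**Do the two follow-up clauses close the gap?** The return-visit clause acts when related events persist or the investigator already has a concern. Note 2 acts when an adverse event needs assessing. Each extends follow-up of something already raised; neither schedules a question that would find a new event.

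**The case against.** The strongest objection is that the supplied protocol is only a synopsis. The SAP cites a protocol dated 08 August 2017 with a double-blind title, and an ITT definition that the synopsis lacks. The 28-day rule and the relatedness categories in SAP 7.1 are also absent from the synopsis. Serious-AE procedures would normally be in the fuller text. This stands as a limit: the point holds for the visible schedule, and the sponsor can answer it by citing such a procedure.

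Note 2 is attached to the call, which suggests that adverse events may come up there. That is fair, but it does not supply a listed question.

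The expected number of events is small, and the trial has no inferential analysis (SAP 2.2). That stands too. It limits the importance of the point, but the remedy is nearly free.

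Several stronger readings are tempting and are not supported:
- *That SAP 7.1 contradicts the schedule.* Capture can include spontaneous reports, so the two are compatible.
- *That late serious events cannot be told apart from on-treatment ones.* Table 14.3.1.1 pools them, but the AE listing (16.2.7) is sorted by start and stop date (SAP Table 10.1.2), and Listings 16.2.10 and 16.2.11 cover telephone contacts and visit dates. Non-serious capture stops at the last application, so any later onset comes from the serious-AE window.
- *That subjects are given no instruction to report late events, or that the table has no footnote.* Neither absence can be shown: the full protocol and consent text are not visible, and SAP 10.0 puts the table shells in a separate document.
- *That a definite share of events is lost.* This depends on how many unsolicited events get reported, which the documents do not give.

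**Conclusion.** The point holds in a limited form. In the visible schedule, serious AEs that start after Day 42 have no scheduled solicitation, although the SAP's window runs to about Day 70 (Day 68 to 72 with the visit window). That is 28 of 70 days without an AE query, 21 of them without any contact. The consequence is possible under-ascertainment of unreported events; those that are reported can be dated and placed.

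The conclusion rests on treatment to Day 42, on the synopsis listing everything the call asks, and on no fuller serious-AE procedure in text not supplied. Fewer than one event is expected in the window at the assumed rates. Safety evidence for the 42 days of use, which is what the primary objective concerns, is unaffected. It is a modest point, worth acting on because the change is so cheap.

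**What to change.** 1. Add an item to the Day 49 call (protocol, Follow-up Call; SAP 2.1): *Query for serious adverse events since the last visit.*
2. Keep the 28-day window in SAP 7.1 for events that are reported. Shortening it would discard information.
3. State with the serious-TEAE and death counts in Table 14.3.1.1 that events were solicited up to the Day 49 call and spontaneously reported from then until 28 days after therapy. For subjects whose call was made before the change, the statement should say Day 42.

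The cost is one extra question on each of up to 72 calls already planned, with no new visit or call. The question leaves about 21 of the 28 days unsolicited (17 to 25 with the windows), so the table statement is needed in any case. Its downside is a slightly less favourable description of completeness. SAP 3.3 shows that medication use had been reviewed before unmasking, so the question may come too late for some subjects; the table statement can still be added. If the full protocol already contains a serious-AE contact after Day 42, cite it in SAP 7.1 and word the table statement to match.
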